What is the prevalence of the overactive bladder among Egyptian medical students, how can this affect their quality of life, and what are the risk factors that can increase its prevalence?

Hypothesis

We hypothesize that overactive bladder is a common condition in Egyptian medical students.

Aim:

Improve the quality of life of medical students by addressing the prevalence of overactive bladder and its risk factors

Objective

- To assess the prevalence of overactive bladder among Egyptian medical students.
- To assess its effect on their quality of life
- To address the risk factors that can increase the prevalence of this condition.

Methodology

A. Technical design

- **Study design:** Analytical cross-sectional study
- **Study sitting:** a medical student in Egypt will be accessed through an online questionnaire.
- **Study population:** Egyptian Medical students studying medicine in Egypt.
- **Time:** 2025-2026
- **Inclusion criteria**
 - Medical student studying human medicine in Egypt
 - Their age ranges from 18 to 27 years old
 - Egyptian person
- **Exclusion criteria**
 - Incomplete data
 - Wrong data in the questionnaire
 - Students refuse to participate

- **Sampling**

We calculated the sample size based on the total medical students in Egypt, which is 121,320, according to the Central Agency for Public Mobilization and Statistics (CAPMAS) 2023-2024(*Capmas*, n.d.). The expected prevalence of overactive bladder is 50%(Abuorouq et al., 2024; Shawahna et al., 2021). Using the total sample size, expected prevalence rate, an 80% power, 95% confidence interval (95% CI), and a 5% error margin, we calculated the sample size via Epi Info version 7.2.60(*Epi InfoTM | CDC*, n.d.) to become 384, and adding a 10% non-response rate, the final sample size will be 422 students

- **Sampling techniques:** The convenient sampling will be applied in this study

B. Operational design

- **Pilot study:** We will perform a pilot study to assess the readability of the questionnaire. We will perform it on 40 students, and any changes in the questionnaire will be made. Pilot study data will be excluded from the data analysis
- **Study field:** an online questionnaire will be shared through social media platforms such as WhatsApp, Facebook, or Telegram.

Data collection method

Students are required to fill out the online questionnaire. It is divided into three main categories.

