1. Sociodemographic data in which we ask about students' age, sex, and academic year. We also ask about their life risk factors, such as body weight, presence of chronic disease, previous surgery, stressful life, and soft drinks(Abuorouq et al., 2024).
2. Questions about the presence of overactive bladder symptoms.(Coyne et al., 2015) The questions are taken from the 6-item ask about the presence of overactive bladder symptoms in the past 4 weeks

This scale consists of 6 items, and each one has 6 available answers that range from not at all, which indicates the absence of the symptoms, to a very great deal, which indicates the presence of these symptoms. The score of each question ranges from 1 to 6, and the total score is 36. A score of 18 or more indicates the presence of the overactive bladder symptoms

3. Part 3 asks about the quality of life affected by the overactive bladder. This part is taken from the quality of life questionnaire part of the Overactive Bladder Symptom and Health-Related Quality of Life Short-Form (OAB-q SF)(Coyne et al., 2015). This is a 13-item questionnaire, each one has 6 answers (None of the time, a little of the time, some of the time, A good bite of the time, Most of the time, All of the time). Each question scores from 1 to 6, so the total score ranges from 13 to 78

- **Statistical analysis**

We will summarize the data first according to its type. Categorical data will be summarized into numbers and percentages, while continuous data will be assessed for normality first; if it is normally distributed, we will use mean and standard deviation (SD), and if not, median and interquartile range will be used (IQR).

Differential statistics will be conducted via the Mann-Whitney U test. We will assess the difference between the baseline data, such as sex, academic year, on the overactive bladder prevalence and its effect on quality of life.

Also, we intended to perform a logistic regression to assess the relation between overactive bladder symptoms and quality of life, and the relation between risk factors, such as history of UTI, soft drinks, coffee, or tea, on the presence of overactive bladder symptoms.

All statistics will be conducted using SPSS version 29.

C. Administrative design

- **Ethical considerations**

- The study protocol will be approved by the Institutional Review Board of Zagazig University, Faculty of Medicine
- Study participants will be included after informed consent.

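### The questionnaire as described names no university or faculty item, so the spread of a national convenience sample over Egypt's medical faculties could not be shown

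*Protocol*

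**What the plan says.** The first objective is national: "To assess the prevalence of overactive bladder among Egyptian medical students". The study population is given as "Egyptian Medical students studying medicine in Egypt", and the Sampling paragraph sizes the study against the "total medical students in Egypt, which is 121,320".

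On recruitment, the Sampling techniques line states "The convenient sampling will be applied in this study", and the Study field line adds that "an online questionnaire will be shared through social media platforms such as WhatsApp, Facebook, or Telegram". There is no list of sites, no quota by faculty and no sampling frame.

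Item 1 of the Data collection method describes the sociodemographic content of part 1 of the questionnaire, and then turns to risk factors: "age, sex, and academic year. We also ask about their life risk factors". The sociodemographic list is written as complete. The risk-factor list that follows is given as examples only: "such as body weight, presence of chronic disease, previous surgery, stressful life, and soft drinks". University, faculty, governorate and recruitment channel are not named as collected items anywhere. The only institution mentioned is the one whose review board approves the protocol. The Statistical analysis paragraph gives sex and academic year as examples of grouping variables and does not mention university or clustering.

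**The concern.** With no frame, quota or site list, the respondent's own answer is the only route described by which the investigators could learn where respondents study. If the question is not asked, two things are lost.

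- **Coverage.** A sample drawn mostly from one or two faculties would look the same in the data as one spread over the country, and either would be reported as the figure for Egyptian medical students.
- **Precision of the prevalence.** The sample size treats answers as a simple random sample. If symptoms differ between universities, the interval for the prevalence will be too narrow, and the data will not allow this to be examined.

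This is not something to leave to a statistical analysis plan. Such a plan can choose a model, but it cannot recover a variable that was never collected.

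**Working it through.** **1. The plan's own figure.** Inputs from the Sampling paragraph: expected prevalence p = 0.50, margin d = 0.05, 95% confidence, population N = 121,320, non-response 10%.

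- n = z² p(1 − p)/d² = 1.96² × 0.25/0.0025 = 384.1
- with the finite population correction, n/(1 + (n − 1)/N) = 382.9
- 384 × 1.10 = 422.4

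The stated 384 and 422 are reproduced. The formula is the one for simple random sampling, that is, a design effect of 1. With 384 analysed, the half-width is 1.96 × √(0.25/384) = 5.0 points. (The 80% power also quoted in that paragraph plays no part in a precision formula.)

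**2. Prevalence interval if answers cluster by university.** The documents give neither the number of universities reached (k) nor an intraclass correlation (ICC), so both are assumed here, with equal numbers per university.

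- m = 384/k
- design effect = 1 + (m − 1) × ICC
- half-width = 1.96 × √(0.25 × design effect/384)

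Example, k = 10 and ICC 0.05: m = 38.4; design effect = 1 + 37.4 × 0.05 = 2.87; effective sample = 384/2.87 = 134; half-width = 5.0 × √2.87 = 8.5 points.

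| Universities (assumed) | Students each | Design effect at ICC 0.01 / 0.02 / 0.05 | Effective sample | Half-width, points |
|---|---|---|---|---|
| 5 | 76.8 | 1.76 / 2.52 / 4.79 | 218 / 153 / 80 | 6.6 / 7.9 / 10.9 |
| 10 | 38.4 | 1.37 / 1.75 / 2.87 | 279 / 220 / 134 | 5.9 / 6.6 / 8.5 |
| 20 | 19.2 | 1.18 / 1.36 / 1.91 | 325 / 282 / 201 | 5.4 / 5.8 / 6.9 |

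With 30 universities the half-width would be 5.3 to 6.3 points.

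**3. Risk factors.** The design effect above is for a proportion. For a covariate that varies within universities (sex, coffee, soft drinks), the variance inflation is roughly 1 + (m − 1) × ICC of the covariate × ICC of the outcome. With m = 38.4 and both set at 0.05, this is 1 + 37.4 × 0.0025 = 1.09, against 2.87 for the prevalence. On the standard error that is a factor of √1.09 ≈ 1.05, against √2.87 ≈ 1.69.

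**4. Coverage.** No arithmetic is needed. Without a university variable, the share of answers from any faculty is unknown whatever the ICC is.

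**The case against.** The strongest reply is that the questionnaire itself is not shown and that its description is incomplete elsewhere. History of urinary tract infection, coffee and tea are to be analysed but are not listed among the items. Egyptian nationality and the study of human medicine are required for entry, yet no question on either is described. A university item may therefore exist. This stands: the text supports only that no such item is named, not that none will be asked. Against that, the list where the item belongs is written as closed, so anyone building the form from the protocol would leave it out.

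A reader might go further and infer three things that the documents do not support.

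- *That answers will arrive in blocks from the same faculty through peer groups.* The protocol names social media platforms and convenience sampling. Block recruitment is plausible but not stated.
- *That the risk-factor standard errors will be too small by the same factor as the prevalence.* Step 3 of the working shows that this carries the design effect of a proportion over to covariates that vary within universities, where the inflation is small.
- *That recording university would make the national estimate sound.* The main weakness of a convenience sample is self-selection, and neither the item nor clustered errors would remove it.

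It is also fair to say that the half-widths depend wholly on the assumed inputs. At 20 universities and an ICC of 0.01 the loss is only 0.4 point, and nothing in the protocol says which end of the range applies. Lastly, with 5 to 10 universities, cluster-robust errors and random-intercept variances are themselves poorly estimated. None of this touches the coverage argument.

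**Conclusion.** The point holds as a gap in the described data collection. A national prevalence is to be reported from a convenience sample, and the description of the questionnaire names nothing that would show where respondents study. If the form follows that description, the spread over faculties cannot be described and clustering by university cannot be checked, and both losses are permanent once the survey closes.

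The coverage part rests on the text alone. The precision part is an illustration: about 5.4 to 10.9 points in place of 5.0, for the prevalence only, under 5 to 20 equally sized universities and an assumed ICC of 0.01 to 0.05. Whether symptoms do differ between universities is unknown. The study can run without the item, but its national claim could not then be examined. Because the remedy is so cheap, it should be adopted before release.

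**What to change.** In part 1 of the questionnaire, add one required item on university or faculty of medicine, and name it in the Data collection method. If the form already has it, naming it in the protocol is enough. The 40-student pilot already allows for changes to the questionnaire, so this can be done before the link is released.

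Then:

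- report the distribution of respondents by university;
- give the prevalence again with the largest-contributing faculty left out;
- if enough universities contribute, give a university-clustered interval for the prevalence beside the simple one;
- say in the report that the item describes coverage and does not make the convenience sample representative.

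The cost is one extra question, a short addition to the analysis, and possibly a wider interval for the prevalence.

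### Comparing the bladder-specific quality-of-life score by sex and academic year, with no restriction to students with overactive bladder, mixes prevalence with impact

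*Protocol*

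**What the plan says.** The second objective in the protocol's Objective list is "To assess its effect on their quality of life", where the condition meant is overactive bladder.

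The only quality-of-life measure is part 3 of the questionnaire (Data collection method), the 13-item quality-of-life part of the OAB-q SF. The protocol describes it in these words: "Part 3 asks about the quality of life affected by the overactive bladder". On scoring it says: "Each question scores from 1 to 6, so the total score ranges from 13 to 78".

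Part 3 belongs to a single form for everyone: "Students are required to fill out the online questionnaire. It is divided into three main categories". No skip rule is given, and "Incomplete data" is an exclusion criterion, so a student who left part 3 blank would drop out of the analysis. Cases are defined from the symptom part: "A score of 18 or more indicates the presence of the overactive bladder symptoms".

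The Statistical analysis section names the Mann-Whitney U test for group differences and continues, in a sentence quoted here without its final word: "We will assess the difference between the baseline data, such as sex, academic year, on the overactive bladder prevalence and its effect on quality of". It names no subset and no adjustment for this comparison. Separately, it plans a logistic regression relating overactive bladder symptoms to quality of life.

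**The concern.** A score built to record what bladder symptoms do to daily life should be low in students who have few such symptoms. Averaged or ranked over a whole group, it reflects two things at once: the share of the group that are cases, and how badly those cases are affected. The protocol lists prevalence and effect on quality of life as two separate results by sex and academic year, but over all students the second partly restates the first.

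The study could therefore report that women, or students in a given year, suffer a greater quality-of-life effect of overactive bladder when their cases are no worse off and there are simply more of them. These are different messages, and a reader would take the second result as additional evidence.

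**Working it through.** **The plan's own figures.** The protocol gives no figure for this comparison. Its sample size is used below only to set the size of a survey: 1.96² × 0.5 × 0.5 / 0.05² = 384.16, which reproduces the stated 384. Half of that is 192 per sex; an equal split by sex is an assumption.

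**Mechanism.** Let p be the proportion of cases in a group, and let the mean scores be C in cases and N in non-cases, the same in both groups. The all-student mean is p·C + (1 − p)·N. The difference between two groups is then (p₁ − p₂) × (C − N). It is zero only if prevalence is equal or cases and non-cases score alike. Impact among cases does not differ at any point in this calculation.

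**Numbers put in.** None of the score values or prevalences by sex is in the protocol, so two sets of scores are shown.

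- Wide gap (C = 40, N = 16). At 60% and 40%: 0.6×40 + 0.4×16 = 30.4 and 0.4×40 + 0.6×16 = 25.6, a difference of 4.8 points. At 55% and 45%: 0.10 × 24 = 2.4 points.
- Narrow gap (C = 30, N = 20). At 60% and 40%: 0.20 × 10 = 2.0 points. At 55% and 45%: 0.10 × 10 = 1.0 point.

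**How often the planned test would call this significant.** Surveys were simulated with 192 students per sex, scores limited to 13–78, a two-sided Mann-Whitney test at 5%, and identical score distributions in the two sexes within cases and within non-cases.

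| Assumed scores, mean (SD) | 60% v 40% | 55% v 45% | 50% v 50% |
|---|---|---|---|
| Cases 40 (12), non-cases 16 (3) | 87–90% | 35–37% | about 5% |
| Cases 30 (12), non-cases 20 (7) | about 43% | about 15% | about 5% |

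The ranges in the first row come from repeated runs.

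A differently built simulation used 384 students, a non-case mean of 25, SD 10 throughout, and cases higher by 10, 20 or 30 points. It gave 42%, 81% and 91% at 60/40, and 14%, 28% and 38% at 55/45. At 50/50 it stayed at 4–5%. With no gap between cases and non-cases it stayed near 5% even at 60/40. The signal therefore needs both a prevalence difference and a score gap, as the formula says.

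**Does restricting to cases remove it?** Under the wide-gap assumptions, the same test among cases only rejected in about 4% at 60/40, 6% at 55/45 and 4% at 50/50, which is its nominal level within simulation error.

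**The case against.** Four counter-arguments deserve weight.

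*The second objective does not rest on the sex and year comparison.* This is correct. The logistic regression of symptoms and quality of life is the analysis aimed at it. A reader might infer that the protocol has no means of addressing the objective; the Statistical analysis section does not support that. The regression does not repair the group comparison, however. Its association is also partly built in, because both scores are bladder-specific and the protocol takes them from the same cited source.

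*The analysis set is not stated, and the effect of the condition could be read as impact among those who have it.* That reading is possible. But the protocol states no restriction, all students complete part 3, and incomplete forms are excluded, so every analysed student has a score. The all-student comparison is the natural execution of the text.

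*The size depends on assumed scores.* This stands. A non-case is anyone scoring 6 to 17 on six items, so up to 17/6 = 2.8 per item, and may have real symptoms. Non-cases need not sit near the floor of 13. The narrow-gap row allows for this and roughly halves the rejection rate at 60/40.

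*The score by group is not merely prevalence again.* This also stands. With equal prevalence and an assumed 8-point difference among cases, the all-student test rejected in about 39% of simulations, against 99% within cases. A reader might infer that the comparison only duplicates the prevalence result; that holds only if impact among cases is similar across groups. Otherwise the comparison carries extra information, diluted and mixed with prevalence.

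A reader might also infer that the study claims to measure general quality of life. It does not: the protocol openly describes part 3 as condition-specific, and condition-specific impact is a legitimate target.

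**Conclusion.** The point holds for the sex and academic-year comparisons of the 13–78 score. As written, with no restriction to cases and no adjustment for symptom status, they cannot separate a difference in prevalence from a difference in impact.

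The consequence is material if prevalence differs between groups and negligible if it does not. The sizes are illustrations, because the protocol gives neither prevalence by sex in Egyptian medical students nor any expected score. They assume equal impact among cases and two equal groups; academic years would form smaller groups, which were not simulated.

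The prevalence estimate itself is unaffected. The change should be made, but it concerns the interpretation of secondary comparisons and not the validity of the survey.

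**What to change.** In the Statistical analysis section:

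1. Report the distribution of the 13–78 score among students scoring 18 or more on the symptom part, and make the sex and academic-year comparisons of the score within those students.
2. Keep the all-student comparison as secondary and labelled as such, or adjust it for symptom score. Adjustment retains students who have symptoms below the threshold.
3. Describe the symptom and quality-of-life regression as an association with bladder-related impact.

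The cost is wording only; all the data are already to be collected. The price is precision: at the expected 50% prevalence, about 0.5 × 384 = 192 students remain for the case-only comparisons, so intervals widen. The case-only analysis also says nothing about impact in sub-threshold students, which is the reason to keep an adjusted all-student analysis beside it.

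### For overactive bladder itself, the plan names only the yes/no split at 18 as the outcome of its group and risk-factor analyses and gives a rank test to that split; the 6–36 symptom score is not named as an outcome

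*Protocol*

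**What the plan says.** Protocol, B. Operational design, Data collection method, item 2, describes six symptom items: "The score of each question ranges from 1 to 6, and the total score is 36". The lowest possible total, 6, is implied. The total is then divided: "A score of 18 or more indicates the presence of the overactive bladder symptoms".

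The Statistical analysis section names one between-group test, Mann-Whitney U, and continues: "We will assess the difference between the baseline data, such as sex, academic year, on the overactive bladder prevalence". The same sentence goes on to the effect on quality of life, which is a separate 13–78 score. A logistic regression then relates risk factors such as urinary infection history, soft drinks, coffee or tea to an outcome worded "on the presence of overactive bladder symptoms". That regression sentence also covers the relation between symptoms and quality of life, without saying whether symptoms enter as a score or as yes/no.

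Under A. Technical design, Sampling, the size is set from the expected prevalence and "an 80% power, 95% confidence interval (95% CI), and a 5% error margin", and comes "to become 384, and adding a 10% non-response rate, the final sample size will be 422 students". The third objective concerns risk factors that raise the prevalence of the condition.

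**The concern.** The questionnaire yields a total from 6 to 36, but wherever a group or a risk factor is compared on overactive bladder, the outcome named is prevalence or presence. A student scoring 17 is then counted with one scoring 6, and a student scoring 18 with one scoring 36.

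The named test makes this harder to read. Mann-Whitney U compares ranks and suits a score. On a yes/no variable there are only two tied ranks, and the test becomes a comparison of two proportions. Either the authors meant the score and did not say so, or they meant prevalence and chose a test that gains nothing there. An analyst could follow the text either way and report different results.

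At stake is power for the sex, academic-year and risk-factor comparisons on overactive bladder. The sample size was set for one prevalence estimate, so nothing in it protects those comparisons.

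**Working it through.** **1. The plan's own figure.** Inputs from Sampling: p = 0.50, margin d = 0.05, z = 1.96, population 121,320.

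- n = z²p(1−p)/d² = 3.8416 × 0.25 / 0.0025 ≈ 384.
- With the finite population correction, 382.9.
- With 10% added, 384 × 1.10 = 422.4, the stated 422.

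The figure reproduces. The stated 80% power plays no part in this formula, so the study is not sized for any comparison.

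**2. Mann-Whitney on a yes/no outcome.** With only two values, the tie-corrected statistic (squared, no continuity correction) equals Pearson's chi-square × (N−1)/N. For N = 384 the factor is 383/384 = 0.997, so the two tests are practically the same.

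**3. Information kept by the split if a factor shifts the whole score.** The Protocol gives no score distribution, so two shapes are assumed:

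- Logistic score, split v rank or proportional-odds analysis: 3p(1−p).
- Normal score, split v t-test: φ(c)²/[p(1−p)], where c is the cut-off in SD units.
- Normal score, split v Mann-Whitney: the previous value divided by 3/π = 0.955.

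At p = 0.50:

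- Logistic: 3 × 0.25 = 0.75; 384 × 0.75 = 288.
- Normal v t-test: 0.3989²/0.25 = 0.637; 384 × 0.637 ≈ 244.
- Normal v Mann-Whitney: 0.637/0.955 = 0.667; 384 × 0.667 ≈ 256.

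The same formulas at lower prevalences cited in the Protocol's background, with the effective number out of 384 in brackets:

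| Prevalence | Logistic v ordinal | Normal v Mann-Whitney | Normal v t-test |
|---|---|---|---|
| 50% (expected) | 0.750 (288) | 0.667 (256) | 0.637 (244) |
| 16% (USA, general population) | 0.403 (155) | 0.461 (177) | 0.440 (169) |
| 6% (Chinese university students) | 0.169 (65) | 0.263 (101) | 0.252 (97) |

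**4. The same loss as power.** Assume two equal groups of 192 and a normal score. The shift that a t-test on the score detects with 80% power is (1.960 + 0.842) × √(2/192) = 0.286 SD. Centred on 50% prevalence, this shift gives 44.3% v 55.7%, which the yes/no comparison detects with about 61% power. At 16% prevalence the figure is about 46%, and at 6% about 28%. A simulation with a rounded 6–36 score (assumed SD 6) gave 78% for Mann-Whitney on the score v 60% for the split at 50% prevalence, and 77% v 48% at 18%.

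**5. The opposite case.** Assume instead that a factor changes only the proportion of cases, with scores among cases and among non-cases unchanged. With 192 v 192 and 2,000 simulated trials, Mann-Whitney on the score v chi-square on yes/no gave 66% v 78% power for 44% v 58% prevalence, and 42% v 80% for 10% v 20%. Here the yes/no analysis is better. The direction of the difference therefore depends on how risk factors act, and the Protocol does not say.

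**The case against.** The strongest defence is that the yes/no outcome is the one the study is about. The third objective is framed as prevalence, and logistic regression on case status estimates that directly. A score model answers a related but different question, symptom burden, including variation between 6 and 17 among students who are not cases. This stands: the score analysis can supplement the logistic model but should not displace it.

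Second, the authors may already intend Mann-Whitney for the scores, because the test makes little sense for a prevalence. That is possible. But the sentence names prevalence as the bladder outcome, no sentence names the symptom total, and a clarification is needed under either reading.

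Third, a reader might infer that every association in the study depends on the cut-off at 18. The text does not support that. The group comparisons also cover the 13–78 quality-of-life score, which is not split, and the regression of symptoms with quality of life does not say which form of the symptom variable it uses.

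Fourth, a reader might infer that the score is always the more sensitive outcome. It is not: step 5 of the working shows the reverse under a different but plausible mechanism.

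**Conclusion.** The point holds for overactive bladder itself. The bladder outcome named for the sex and academic-year comparison and for the risk-factor model is only the split at 18, and a rank test is assigned to that split. The mismatch between test and outcome is the firmest part, because it follows from the text alone.

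The loss of information is conditional. For a shift of a normal or logistic score it is about 25–33% at the expected 50% prevalence against a rank or ordinal analysis, and 36% against a t-test. It rises to 54–60% at 16% and 74–83% at 6%. Those two prevalences come from other populations and show sensitivity only; they are not forecasts for this study. The power figures also assume equal groups of 192. If risk factors change only the proportion of cases, there may be no loss at all.

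This is worth correcting before data are analysed, but it does not threaten the prevalence estimate.

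**What to change.** - Keep prevalence at the 18-or-more cut-off for objective 1, and the logistic model as the main risk-factor analysis for objective 3.
- State that prevalence is compared between groups by chi-square, and that Mann-Whitney applies to the 6–36 symptom score and the 13–78 quality-of-life score. Where a factor such as academic year is kept in more than two categories, name the multi-group rank test.
- Add a pre-specified supplementary proportional-odds or linear model of the 6–36 score with the same risk factors, reported beside the logistic model. Do not describe it in advance as the more sensitive analysis.

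The cost is one extra model and one table column, with no new data. There is also a second set of association tests, which must be labelled supplementary so that it does not compete with the main model, and the proportional-odds or linear-model assumptions need checking. The supplementary effects will be cumulative odds ratios or score points rather than effects on prevalence, so both sets must be shown.

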Several studies have assessed the prevalence of overactive bladder among different population age groups, ethnicities, or genders with varying results. It was rated to be 11.8% in a multicenter cross-sectional study including several countries in Canada and Europe (Germany, Italy, Sweden, and the UK (Irwin et al., 2006), while in the USA it was estimated to be 16% (Stewart et al., 2003). All these studies were conducted on the general population; however, in China, it was about 6% among university students (Liang et al., 2022).

In the Arab world, several cross-sectional studies have also assessed the prevalence of overactive bladder, including students, and its effect on the quality of life. Hajjar 2022 (Hajjar et al., 2022) assessed its prevalence among Lebanese female nulliparae university students. They showed that nocturia and frequency were the most common symptoms that bothered students. They also found a statistical correlation between smoking, drinking coffee, or tea, and increased symptoms. Also, drinking soft drinks was associated with an increase in urinary leakage. Additionally, Abuorouq 2024(Abuorouq et al., 2024) and Shawahna 2021(Shawahna et al., 2021)

Cross-sectional studies were conducted on medical students in Jordan and Palestine, respectively. They reported a prevalence of 44.5% and 54.1%, respectively. Shawahna 2021(Shawahna et al., 2021) reported a statistically significant correlation between gender or stressful life and a decrease in quality of life.

Rational

In Egypt, the prevalence of overactive bladder is underestimated. A single previous multinational cross-sectional study across several Arab countries, including Egypt, was conducted. (Al Edwan et al., 2021) was conducted in Egypt, Algeria, Jordan, and Lebanon among women. They reported a prevalence of 57.5% among Egyptian women.

Since this study, no study has been conducted to further assess its prevalence in different age or gender groups in Egypt. Taking into consideration the stressful life of medical students in Egypt, and several life risk factors they face, we will conduct this cross-sectional study.

No previous cross-sectional study was conducted on the medical students in Egypt before.

We aim to assess the prevalence of overactive bladder among Egyptian medical students. We will also assess the risk factors associated with an increase in this condition and its effect on their quality of life.

Research Questions

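### The objective asks how much overactive bladder changes quality of life, but the planned logistic regression cannot report a difference in the 13-78 score

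*Protocol*

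**What the plan says.** Under Objective, the second aim is "To assess its effect on their quality of life", where the condition meant is overactive bladder (OAB). Under Data collection method, item 2 makes OAB a yes/no variable: "A score of 18 or more indicates the presence of the overactive bladder symptoms". Item 3 sums 13 questions for quality of life, "so the total score ranges from 13 to 78", and gives no cut-off.

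The Statistical analysis section links the two in one clause: "we intended to perform a logistic regression to assess the relation between overactive bladder symptoms and quality of life". The same sentence then uses the same method for "the relation between risk factors, such as history of UTI, soft drinks, coffee, or tea, on the presence of overactive bladder symptoms", where the outcome is binary and logistic regression fits.

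The only other inferential method is the Mann-Whitney U test. Its sentence says the team will assess "the difference between the baseline data, such as sex, academic year, on the overactive bladder prevalence and its effect on quality of life". No linear, ordinal or other model with the quality-of-life score as outcome is given.

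**The concern.** The objective has a direction: OAB is the exposure and quality of life the outcome. Logistic regression needs a binary dependent variable, and the quality-of-life score is not one. The clause therefore allows two models, and neither answers the objective.

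- **OAB as outcome, score as predictor.** The result is the odds of OAB per quality-of-life point, which turns the objective round.
- **Score split into two classes.** This needs a cut-off that the protocol does not give, loses precision, and still yields no difference in score.

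Either way, the report would not say how far quality of life differs between students with and without OAB. Adjustment matters too. The introduction cites a study of medical students that "reported a statistically significant correlation between gender or stressful life and a decrease in quality of life", so a crude comparison may mix the contribution of OAB with that of sex and stress. Both are already in the questionnaire.

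**Working it through.** **Inputs from the protocol.** Score range: 13 x 1 = 13 to 13 x 6 = 78. OAB is binary at a symptom total of 18. Expected prevalence is 50% (Sampling). The introduction says of the Jordanian and Palestinian student studies: "They reported a prevalence of 44.5% and 54.1%, respectively".

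**The plan's own sample size.** n = 1.96² x 0.5 x 0.5 / 0.05² = 384.1, or 382.9 with the finite-population correction for 121,320 students. The protocol states 384. Then 384 x 1.10 = 422.4, against 422 stated. Both reproduce. At 50% prevalence, 384 students give 192 v 192.

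**Assumptions.** The protocol gives no SD or expected difference for the score. I take within-group SDs of 8, 10, 12 and 15, normality and equal variance, without covariates.

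**Which model is meant?** OAB already has a cut-off and is the outcome in the second half of the same sentence. The score has none. OAB as outcome is the likelier reading.

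**What that model reports.** Under the assumptions, the odds ratio (OR) per point is exp(difference / SD²), so difference = ln(OR) x SD². With ln(1.05) = 0.0488:

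| SD | Difference implied by OR 1.05 | OR for a 5-point difference | 95% CI half-width, linear model |
|---|---|---|---|
| 8 | 0.0488 x 64 = 3.1 | exp(5/64) = 1.081 | 1.61 |
| 10 | 0.0488 x 100 = 4.9 | exp(5/100) = 1.051 | 2.01 |
| 12 | 0.0488 x 144 = 7.0 | exp(5/144) = 1.035 | 2.41 |
| 15 | 0.0488 x 225 = 11.0 | exp(5/225) = 1.022 | 3.01 |

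The last column is t(382) x SD x sqrt(2/192). At prevalences of 44.5% (171 v 213) and 54.1% (208 v 176) it changes by at most 0.02. Simulation of the reversed logistic model (2,000 runs per SD, true difference 5 points) gave ORs of 1.082, 1.052, 1.036 and 1.023. The mean difference was 5.0 each time.

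**Power.** Two score shapes were simulated at 192 v 192: a normal score (5,000 runs) and a floor-skewed score (4,000 runs). The skewed score was 13 + exp(N(2.0 + m, 0.85)), rounded and held to 13-78. At m = 0 it has mean 23.5, SD 9.9 and skewness about 2.5. Power at a difference of 0.30 SD:

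| Model | Normal score | Floor-skewed score |
|---|---|---|
| Linear (robust HC3 errors for the skewed score) | 83.3% | 85.8% |
| Reversed logistic | 83.1% | 85.2% |
| Score split at the median | 64.5% (Wald formula) | 78.4% |

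The reversed model costs no power. A median split would: its efficiency under normality is 2/π = 0.637, a loss of about 36% of the information. The protocol does not say the score will be split, so that row is only a contingency.

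**Does the linear model survive skew?** With the skewed score and HC3 errors, 95% CI coverage over m = 0 to 0.6 was 94.3% to 95.7% at prevalences of 44.5%, 50% and 54.1%. If OAB were much rarer than planned, coverage would fall to about 92-93% at 10% (38 students with OAB) and 91-92% at 6% (23 students).

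**The case against.** The strongest reply is that the Mann-Whitney sentence already covers the objective. Its closing words come close to repeating it, sex and academic year are only examples, and a Mann-Whitney comparison of the score by OAB status would have the right direction. The sentence is loose enough to make this arguable. It still never names OAB status as the grouping variable, its subject is baseline factors, and the test would give no adjusted estimate.

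A second reply is that the clause does not name the dependent variable, and that variable roles may be left to a statistical analysis plan. The first part stands: the reversal belongs to the likelier reading, not to a stated one. The second does not help, because the protocol itself fixes the method as logistic, and no choice of dependent variable under it yields a difference in score.

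A third is that the harm is modest. The reversed model is a valid test of association, and a cross-sectional survey cannot establish direction whichever variable is on the left. That also stands. What is lost is the quantity the objective asks for, not the ability to detect an association. The SDs above are assumptions and serve to show the size of the ambiguity.

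Finally, the introduction supports only sex and stressful life as covariates for quality of life. Academic year and chronic disease are suggestions drawn from the questionnaire.

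**Conclusion.** The concern holds and should be fixed. The method named for the second objective does not estimate how quality of life differs by OAB status. On the likelier reading it answers the reverse question, on an odds-ratio scale from which the score difference cannot be read without the SD: a 3.5-fold range (11.0 / 3.1) over the SDs assumed here. Power is not affected on that reading, and neither are the prevalence objective and the sample size. Confidence is medium, because the protocol does not name the dependent variable.

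**What to change.** Replace the first half of the regression sentence with:

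> The association of OAB (symptom total at or above 18) with quality of life will be estimated by linear regression with robust standard errors, with the 13-78 total as dependent variable and OAB (yes/no) as exposure, adjusted for prespecified covariates already collected (sex, academic year, chronic disease, stressful life). The adjusted mean difference with its 95% CI will be reported.

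Use this model whatever the skew. Proportional-odds regression may be added as a sensitivity analysis, but should not replace it after the data are seen. If OAB proves far rarer than 50%, note that the interval may be somewhat too narrow.

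Keep binary logistic regression for the risk factors of OAB, without the quality-of-life score among the covariates. If the Mann-Whitney sentence was meant to include a comparison by OAB status, say so there.

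The cost is a wording change in the Statistical analysis section: no new data, no change to the sample size, and the same software (SPSS 29).
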